11.3 Insertion and Removal Related Bleeding and Cramping/Pain

IUS insertion and removal bleeding and cramping/pain related to IUS insertion and removal will be summarized by treatment group. IUS insertion related bleeding and

cramping/pain are recorded on the IUS Insertion Questionnaire. IUS removal related bleeding and cramping/pain are recorded on the IUS Removal Questionnaire.

Summaries of the following will be presented:

- Bleeding (none, spotting, light bleeding, moderate bleeding, heavy bleeding)
- Cramping/pain (none, mild, moderate, severe)

11.4 Menstrual Related Cramping/Pain

11.4.1 Up to Month 24

For the first 24 months of the study. A subject will be defined as having menstrual cramping/pain (dysmenorrhea) TEAE if:

- The subject diary question, “Check box if cramping today is worse than when not using hormones” is marked

AND

- Baseline cramping/pain or dysmenorrhea is the same or worsens from what is indicated on the Menstrual History CRF based on menstrual characteristics when not using hormonal contraception.

If cramping/pain (dysmenorrhea) TEAE is recorded on the Adverse Event CRF and not on the subject diary due to the event being an SAE, results in IUS removal or is not related to the IUS or menstrual condition, the subject will be counted as having a cramping/pain (dysmenorrhea) TEAE. Subject incidence of cramping/pain or dysmenorrhea TEAEs will be described within the overall adverse event incidence summary.

11.4.2 After Month 24

For Months 25 through 121, cramping/pain (dysmenorrhea) TEAEs will be recorded only in the Adverse Event CRF and not determined based on daily subject diary responses. During these months there will be no subject diary for menstrual changes and instead a periodic (every 3 months) form characterizing their cramping and dysmenorrhea will be used. Self-reported cramping and dysmenorrhea TEAEs will be recorded on the Adverse Event CRF.

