7.12.1 Adverse Event CRFs

Specific Adverse Events are recorded on different CRFs.

AEs related to bleeding or cramping/pain

- With insertion - report on the IUS Insertion Questionnaire CRF
- With removal - report on the IUS Removal Questionnaire CRF
- During IUS use
 - Months 1-24:
 - The subject's diary acts as the menstrual bleeding or cramping/pain AE CRF
 - Menstrual bleeding or cramping/pain should also be reported on the general AE CRF only if:
 - Bleeding or cramping/pain are not related to the IUS or a menstrual condition
 - Bleeding or cramping/pain meet serious criteria; an SAE report would also have to be submitted (this exception is due to data system requirements)
 - Bleeding or cramping/pain result in the IUS being removed (this exception is due to data system requirements)
 - Months 25-121
 - Starting at Month 27 (phone contact), study sites will begin to assess menstrual bleeding/cramping for the prior 3 months (from Month 25; the subject will be asked to characterize her bleeding/cramping pattern for the prior 3 months and compare to when she was not using hormonal contraception prior to study entry)
 - Menstrual bleeding or cramping/pain should also be reported on the general AE CRF if:
 - Bleeding or cramping/pain is indicated as worse in severity or frequency than when the subject was not using hormones on the Bleeding/Cramping Form (verify against Menstrual History)
 - Self-reported by the subject for any months not included in the form (e.g., subject missed last contact so no form was completed) and worse in severity or frequency than when the subject was not using hormones (verify against Menstrual History)

- Bleeding or cramping/pain meets serious criteria (see section 7.8)

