Dysmenorrhea (none, mild, moderate, or severe) will be summarized by the number and percentage of days with a particular pattern during each 84 and 90 day interval after enrollment through Month 24. After Month 24 dysmenorrhea will be summarized from the Adverse Events CRF. In addition, dysmenorrhea changes from baseline will be summarized using shift tables. Baseline dysmenorrhea is recorded on the Menstrual History CRF based on menstrual characteristics when not using hormonal contraception.

- **Adverse Events**

The number and percentage of subjects with each adverse event and serious adverse event will be presented by MedDRA system organ class, preferred term, and treatment group. Summaries will also be presented by relationship to the type of IUS or IUS insertion or removal procedure and the severity of the adverse event. All adverse events will be summarized with special attention to those events that may be related to an IUS, including:

- Difficult insertion or removal procedure;
- Perforation of the uterus;
- Dysmenorrhea;
- Low abdominal pain (not classified as dysmenorrhea);
- Uterine infection (including PID); and
- Other urogenital infections

- **Pregnancy Outcomes**

Pregnancy outcomes will be summarized by treatment group using the MITT population as well as listed by subject.

- **Fertility Rates**

Those women desiring pregnancy after leaving the study will be contacted every three months up to one year after IUS discontinuation to record any pregnancy. Kaplan-Meier methods will be used to estimate the probability of pregnancy over time.

- **Menses After IUS Discontinuation**

Those women who elect to use a non-hormonal contraceptive method or no contraception (including those desiring pregnancy) will be followed monthly for up to 3 months after IUS removal/expulsion for the occurrence of menses following IUS discontinuation.

Women who do not menstruate within 3 months following IUS discontinuation will be referred for appropriate evaluation and continue to be followed monthly until menses has occurred or a diagnosis for the cause of the secondary amenorrhea has been established.

Kaplan-Meier methods will be used to estimate the probability of the return of menses over time.

- **Plasma Levonorgestrel Levels**

- Levels over the lifespan of IUS use

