11.2 Adverse Events

Menstrual bleeding and cramping/pain for the first 24 months are recorded in a daily subject diary and not on the Adverse Events CRF (unless the event is an SAE, results in IUS removal or is not related to the IUS or menstrual condition). The subject daily diary has been designed to collect IUS and menstrual bleeding and cramping AEs following insertion of the study IUS. Menstrual bleeding or cramping/pain would only be entered onto the general AE CRF if:

- Bleeding or cramping/pain meet serious criteria; an SAE report would also have to be submitted (this exception is due to data system requirements)
- Bleeding or cramping/pain result in the IUS being removed (this exception is due to data system requirements)
- Bleeding or cramping/pain is not related to the IUS or a menstrual condition.

After 24 months, menstrual bleeding and cramping/pain are recorded on the Adverse Events CRF. Analyses of cramping/pain and bleeding are described below in section 11.6 .

All adverse event summaries will be restricted to treatment-emergent adverse events (TEAE), defined as AEs occurring during or after attempted IUS insertion and those pre-attempted IUS insertion existing medical conditions that worsened during the study up to the subject's last known IUS date of use or, for subjects who have discontinued, through 30 days after the subject's last known IUS date of use. If an AE cannot be determined as treatment-emergent, it will be counted as such.

Verbatim terms on case report forms will be mapped to preferred terms and system organ classes using the Medical Dictionary for Regulatory Activities (MedDRA) dictionary. Each adverse event summary will be displayed by treatment group. Summaries that are displayed by system organ class and preferred terms will be ordered by descending order of incidence of system organ class and preferred term within each system organ class. Summaries of the following types will be presented:

- Overall subject summary of AEs, SAEs, and deaths
- Subject incidence of TEAEs and total number of unique TEAEs by MedDRA system organ class and preferred term.
- Subject incidence of TEAEs by MedDRA system organ class, preferred term, and highest severity. At each level of subject summarization a subject is classified according to the highest severity if the subject reported one or more events. AEs with missing severity will be considered severe for this summary

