- Subject incidence of TEAEs by MedDRA system organ class, preferred term, and closest relationship to IUS (Related/Not Related). At each level of subject summarization a subject is classified according to the closest relationship if the subject reported one or more events. Related will be defined as “Related”, “Probably Related”, or missing. Not related will be defined as “Unlikely Related” or “Not Related”
- Subject incidence of TEAEs by MedDRA system organ class, preferred term, and closest relationship to IUS Procedure (Related/Not Related). At each level of subject summarization a subject is classified according to the closest relationship if the subject reported one or more events. Related will be defined as “Related”, “Probably Related”, or missing. Not related will be defined as “Unlikely Related” or “Not Related”
- Subject incidence of serious TEAEs and total number of unique serious TEAEs by MedDRA system organ class and preferred term

Incidence rates will include in the denominator all subjects in the Safety Population.

Missing Severity or Relationship

Missing severity or relationship to study drug will prompt queries to be sent to the investigators to provide the information. If after query resolution, the information remains missing, the following conventions will be used in summary tables.

- An event with missing severity will be considered Severe.
- An event with missing relationship will be considered related to study drug.

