11.5 Menstrual Related Bleeding

11.5.1 Up to Month 24

For the first 24 months of the study a subject will be defined as having a menstrual Bleeding TEAE if:

- The subject diary question, “Check box if bleeding today is heavier than when not using hormones” is marked

AND

- Baseline bleeding that is the same or worsens from what is indicated on the Menstrual History CRF based on menstrual characteristics when not using hormonal contraception.

If a bleeding TEAE is recorded on the Adverse Event CRF and not on the subject diary due to the event being an SAE, results in IUS removal or is not related to the IUS or menstrual condition, the subject will be counted as having a bleeding TEAE. Subject incidence of bleeding TEAEs will be described within the overall adverse event incidence summary.

11.5.2 After Month 24

For Months 25 through 121, bleeding TEAEs will be recorded only in the Adverse Event CRF and not determined based on daily subject diary responses. During these months there will be no subject diary for menstrual changes and instead a periodic (every 3 months) form characterizing their bleeding will be used. Self-reported bleeding TEAEs will be recorded on the Adverse Event CRF.

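### SAP 11.4.1 counts cramping recorded as non-menstrual as a dysmenorrhea TEAE; 11.5.1 has the parallel rule for bleeding, less explicitly

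*SAP*

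**What the plan says.** SAP 11.4 is headed as menstrual-related cramping/pain. For the first 24 months, 11.4.1 opens with "A subject will be defined as having menstrual cramping/pain (dysmenorrhea) TEAE if" and gives two diary-based conditions: a ticked box for cramping worse than when off hormones, and a comparison with the Menstrual History CRF. A further sentence brings in events on the AE CRF that are not on the diary. It names three reasons for this: the event was an SAE, it led to IUS removal, or it "is not related to the IUS or menstrual condition, the subject will be counted as having a cramping/pain (dysmenorrhea) TEAE".

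SAP 11.5.1 has the same structure. The definition begins "a subject will be defined as having a menstrual Bleeding TEAE if", and the add-on sentence ends "is not related to the IUS or menstrual condition, the subject will be counted as having a bleeding TEAE".

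Both documents explain how an event reaches the AE CRF in this period. Protocol 7.12.1 lists, beside seriousness and removal, "Bleeding or cramping/pain are not related to the IUS or a menstrual condition". SAP 11.2 lists "Bleeding or cramping/pain is not related to the IUS or a menstrual condition".

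Protocol 9.8 names dysmenorrhea as an adverse event of special attention and, as a separate item, "Low abdominal pain (not classified as dysmenorrhea". SAP 11.2 fixes the denominator: "Incidence rates will include in the denominator all subjects in the Safety Population". SAP section 1 says that the SAP prevails over the protocol where the two differ on statistical analysis.

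**The concern.** Of the three routes to the AE CRF, two can carry genuine menstrual events. Serious events and those leading to removal are entered there because the data system requires it, and adding them back to the diary count is sensible. The third route is different in kind: an event takes it because it was judged not to be menstrual or IUS-related. Counting it as dysmenorrhea reverses that judgement.

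At stake is the meaning of two lines in the Months 1-24 adverse event incidence summary. A programmer who follows 11.4.1 as written would report as dysmenorrhea some events that the site recorded as something else. Because the SAP takes precedence, the protocol's distinction between dysmenorrhea and other low abdominal pain would not correct this.

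**Working it through.** There is no planned figure to reproduce. The documents give no expected incidence for either TEAE, and no sample size or precision target depends on one. The check is therefore textual, with arithmetic for direction only.

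**Step 1: trace the routes in Months 1-24.**

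| Cramping/pain event | Where recorded | Counted under SAP 11.4.1 as | Fits the category? |
|---|---|---|---|
| Diary box ticked and history condition met | Diary | Dysmenorrhea TEAE | Yes |
| Menstrual, and serious or led to removal | AE CRF | Dysmenorrhea TEAE | Yes |
| Not menstrual or IUS-related, not serious, no removal | AE CRF | Dysmenorrhea TEAE | No |
| Not menstrual or IUS-related, but serious or led to removal | AE CRF | Dysmenorrhea TEAE | No |

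The fourth row matters for the remedy. The SAE and removal routes carry no relatedness condition, so striking out only the third reason would leave those events in the count.

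**Step 2: the same trace for bleeding.** The routing is identical, but the closing words of 11.5.1 refer to a bleeding TEAE without the word menstrual. The section heading and the opening definition are both about menstrual bleeding, and 11.5.2 uses the shorter term throughout. The parallel reading is the natural one, but it is one step less explicit than for cramping.

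**Step 3: direction.** Let p be the share of women who qualify through the diary or through a menstrual- or IUS-related AE-CRF event. Let u be the share of the remaining women who have an AE-CRF cramping event judged unrelated to the IUS or a menstrual condition. With a fixed Safety Population denominator:

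- counted incidence = p + (1 - p) × u
- excess over p = (1 - p) × u, which is never negative and is zero when u = 0.

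Because u is defined among women who do not otherwise qualify, no independence assumption is needed.

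**Step 4: illustration.** The documents give neither p nor u; all values below are assumptions. Excess in percentage points:

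| p | u = 0 | u = 0.5% | u = 1% | u = 3% | u = 5% |
|---|---|---|---|---|---|
| 10% | 0 | 0.45 | 0.9 | 2.7 | 4.5 |
| 30% | 0 | 0.35 | 0.7 | 2.1 | 3.5 |
| 50% | 0 | 0.25 | 0.5 | 1.5 | 2.5 |

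For example, p = 10% and u = 3% gives 0.10 + 0.90 × 0.03 = 0.127, an excess of 2.7 points. Scaled to the planned enrolment of about 1,910 over all groups, that is 1,910 × 0.027, or about 52 women.

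**Step 5: what is not touched.** SAP 11.6.1 computes the cramping and bleeding summaries from diary entries alone. The Pearl Index does not use these events.

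**The case against.** The strongest defence of the text is that the add-on sentence in 11.4.1 is conditional: it starts from a cramping/pain (dysmenorrhea) TEAE already recorded on the AE CRF. On that reading, abdominal pain of another kind never enters. But the third reason would then describe dysmenorrhea unrelated to any menstrual condition, which contradicts itself. On either reading the clause needs correction.

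A second defence is that TEAEs are all-causality, AE-CRF terms are MedDRA-coded, and SAP 11.2 tabulates related and unrelated events separately. This stands in part: the unrelated events do belong in the overall AE table. It does not justify the dysmenorrhea label, and neither coding nor the relatedness tables undo the counting rule. For bleeding the defence is stronger, since an unrelated bleed counted merely as a bleeding TEAE is mislabelled only through the section's heading and definition.

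A reader might infer more than the documents support:

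- **A known amount of inflation.** There is none, because p and u are assumed. Some women with an unrelated event may already qualify through the diary, whose tick box asks about severity and not cause.
- **Proof from the earlier European LNG20 trial.** The unrelated abdominal colic reported in Protocol 1.2 was an SAE. Under 11.4.1 it would enter by the SAE route, so it does not isolate the disputed clause.
- **Double tabulation.** No passage says that one AE-CRF event is listed under two terms.
- **Loss of comparability with Months 25-121.** Capture changes from diary to AE CRF at Month 24 by design. SAP 11.4.2 and 11.5.2 state no relatedness exclusion either, so the clause is not shown to create a difference.
- **Damage to the dysmenorrhea and bleeding-pattern outcomes as a whole.** Through Month 24 their day-by-interval summaries come from the diary and are not affected.

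**Conclusion.** The rule is wrong as written, with minor severity. SAP 11.4.1 assigns to dysmenorrhea events that reached the AE CRF because they were judged not to be menstrual or IUS-related, and this conflicts with the separate listing in Protocol 9.8. The same fault in 11.5.1 rests on heading and definition more than on the counting sentence itself.

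The direction of the effect is established: upward or zero on the Months 1-24 AE incidence. It exceeds zero only if at least one woman qualifies solely through an unrelated event. The size cannot be determined from the documents; the range of 0 to 4.5 points holds only for assumed p of 10-50% and u of 0-5%. What is affected is a descriptive safety table in a study that plans no formal testing.

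**What to change.** Replace the add-on sentence in SAP 11.4.1 and 11.5.1. An AE-CRF cramping or bleeding event should count toward the dysmenorrhea or menstrual bleeding TEAE only if both conditions hold:

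1. it is menstrual- or IUS-related; and
2. it was entered on the AE CRF because it was an SAE or led to IUS removal.

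Report all other AE-CRF cramping/pain or bleeding, including unrelated SAEs and unrelated events that led to removal, in the all-causality AE table under its own MedDRA preferred term. Keep low abdominal pain separate from dysmenorrhea, as in Protocol 9.8. In 11.5.1, use the term menstrual bleeding TEAE throughout so that the category is unambiguous.

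The cost is a wording change in two subsections and a small programming change, with no new visits or assessments. Causality on the AE CRF is assessed against the IUS and its insertion or removal procedures, so a review of verbatim terms may be needed to establish menstrual relationship.

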11.5 Menstrual Related Bleeding

11.5.1 Up to Month 24

For the first 24 months of the study a subject will be defined as having a menstrual Bleeding TEAE if:

- The subject diary question, “Check box if bleeding today is heavier than when not using hormones” is marked

AND

- Baseline bleeding that is the same or worsens from what is indicated on the Menstrual History CRF based on menstrual characteristics when not using hormonal contraception.

If a bleeding TEAE is recorded on the Adverse Event CRF and not on the subject diary due to the event being an SAE, results in IUS removal or is not related to the IUS or menstrual condition, the subject will be counted as having a bleeding TEAE. Subject incidence of bleeding TEAEs will be described within the overall adverse event incidence summary.

11.5.2 After Month 24

For Months 25 through 121, bleeding TEAEs will be recorded only in the Adverse Event CRF and not determined based on daily subject diary responses. During these months there will be no subject diary for menstrual changes and instead a periodic (every 3 months) form characterizing their bleeding will be used. Self-reported bleeding TEAEs will be recorded on the Adverse Event CRF.

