7.1.7 Menstrual Changes

Women who use a LNG IUS experience a change in menstrual bleeding patterns. Most commonly, women experience irregular bleeding and spotting in the first 3-6 months after

insertion. The average number of days of bleeding and spotting decline over the first year with an average of less than 2 days of bleeding per month by the end of one year (Andersson 1994). Approximately 20% of women are amenorrheic for a period of 90 days or more by the end of the first year of use (Andersson 1994). In a U.S. study, approximately 80% of Mirena users rated their bleeding as much lighter at the end of 12 months of use compared to 4% of subjects who considered their bleeding to be heavier (Jensen). Approximately 70% of women rated the changes in their bleeding as beneficial.

Hemoglobin values increase with LNG IUS use by an average of 2.4 g/dL at 3 months and 1.8 g/dL at 12 months (Luukkainen). The hemoglobin levels then appear to remain stable with a mean increase of 1.6 g/dL at 5 years (Andersson 1994). The increases are related to starting levels as women with a lower hemoglobin initially experience a greater increase (Luukkainen).

Discontinuation because of bleeding problems is reported to occur in approximately 7.3 per 100 women in the first year and 15 per 100 women cumulatively over 5 years (Andersson 1994).

Approximately 4 per 100 women discontinue because of amenorrhea. Such removals may be avoided with better counseling. In a recent US trial, 3.5% of women discontinued Mirena in the first year because of complaints related to bleeding (Jensen). This lower rate may be related to better counseling regarding the expected bleeding or a difference in the subject population.

Possible bleeding changes with the LNG20 in this study are not expected to pose a substantial risk to the subject's health but rather an inconvenience.

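### The bleeding TEAE definition widens at Month 25, from heavier bleeding to worse severity or frequency, yet the SAP reports one incidence with no split

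*SAP*

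**What the plan says.** **Months 1-24.** Protocol 7.12.1 makes the diary the AE record for this symptom: "The subject's diary acts as the menstrual bleeding or cramping/pain AE CRF". SAP 11.5.1 then defines a bleeding TEAE by two conditions joined by AND. The diary item "Check box if bleeding today is heavier than when not using hormones" must be marked, and there must be "Baseline bleeding that is the same or worsens from what is indicated on the Menstrual History CRF". A second route exists: a bleeding TEAE entered on the AE CRF instead of the diary also counts, where this was "due to the event being an SAE, results in IUS removal or is not related to the IUS or menstrual condition".

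**Months 25-121.** SAP 11.5.2 takes bleeding TEAEs from the AE CRF only. Protocol 7.12.1 tells sites to make an entry when "Bleeding or cramping/pain is indicated as worse in severity or frequency than when the subject was not using hormones on the Bleeding/Cramping Form", when the woman self-reports the same worsening for months the form did not cover, or when the event is serious.

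**Reporting.** SAP 11.5.1 states: "Subject incidence of bleeding TEAEs will be described within the overall adverse event incidence summary". SAP 11.2 gives AE incidence the whole Safety Population as denominator. Neither section splits the table at Month 24.

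**When the event is expected.** Protocol 7.1.7 says that, most commonly, "women experience irregular bleeding and spotting in the first 3-6 months after" insertion.

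**The concern.** One row of the AE table is built from two different tests. The test in force early looks at whether bleeding is heavier; the later one also admits frequency. Protocol 7.7 defines an AE to include a pre-existing episodic condition that occurs more often, not only one that becomes more intense. The diary rule is therefore narrower than the protocol's own definition, and SAP Section 1 gives the SAP precedence on analysis discrepancies.

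At stake is the meaning of the bleeding TEAE percentage. A reader will take it as the share of women whose bleeding got worse. For the early months it is closer to the share whose bleeding got heavier, plus those with a serious, removal-causing or unrelated event. The months in which irregular bleeding is expected lie wholly under the narrower test.

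**Working it through.** The documents give no bleeding TEAE rate to reproduce, so the check is a comparison of rules, followed by some arithmetic for scale.

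**Step 1. The two rules side by side.**

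| | Months 1-24 | Month 25 onward |
|---|---|---|
| Source | Daily diary (Protocol 7.12.1, SAP 11.2) | AE CRF (SAP 11.5.2), prompted by a three-monthly form or self-report |
| Test | Heavier box AND menstrual-history condition | Worse in severity OR in frequency |
| Other route | AE CRF entry if serious, leads to removal, or unrelated | AE CRF entry if serious |
| Blank diary day | Treated as no reported bleeding (SAP 5.3.2) | Not applicable |

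**Step 2. Logic.** Let H = heavier box marked, B = menstrual-history condition met, C = AE CRF exception, S = worse severity, F = worse frequency.
- Early TEAE = (H and B) or C.
- Later AE = S or F (or serious).
- A woman with F only (no H, no C) gives early = no, later = yes.

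The SAP does not say exactly what B compares. That does not matter here: with H absent, the AND fails whatever B is.

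**Step 3. A constructed case.** A woman with normal flow at baseline spots or bleeds lightly on 60 of 90 days, never marks the heavier box, and keeps the IUS. In Months 1-24 she has no bleeding TEAE. With the same pattern after Month 24 she has one, if it is more frequent than her history.

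**Step 4. Pooling.** SAP 11.5.1 sends early bleeding TEAEs to the overall summary. SAP 11.5.2 takes later ones from the AE CRF, which SAP 11.2 summarizes over the Safety Population. With no split specified, both land in one percentage.

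**Step 5. Scale.**
- *Women who never meet the wider rule.* Using the planned discontinuation ceilings of 20% and 19% (Protocol 9.1): 1 - 0.80 x 0.81 = 0.352, about 35% by Month 24.
- *What the removal route can catch.* Protocol 7.1.7 cites bleeding-related discontinuation in year 1 of 3.5% to 7.3%, from other studies. Of about 1,600 + 150 = 1,750 LNG20 women: 0.035 x 1,750 = 61 and 0.073 x 1,750 = 128. This route sees only bleeding troublesome enough to end use.
- *Planned time under the wider rule* (Protocol 3.1). Mirena, Months 25-60: 36 of 60 months, 60%. LNG20 36-45, Months 25-96: 72 of 96, 75%. LNG20 16-35, Months 25-121: 97 of 121, 80%. SAP Section 3 keeps Mirena in the AE incidence tables.
- *Illustration, by assumption only.* Let q be the share of women with bleeding worse in severity or frequency by Month 24, and f the share of those with neither the heavier box nor an AE CRF entry. Missed = q x f. For q = 20% to 40% and f = 25% to 75%: 0.20 x 0.25 = 5 points up to 0.40 x 0.75 = 30 points. Neither q nor f is in the documents. A woman missed early but counted later returns to the pooled numerator, so the pooled shortfall would be smaller.

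**The case against.** The best reply is that little information is lost. SAP 11.6.1 tabulates bleeding and spotting days for every 28-day cycle and every 84- and 90-day interval by treatment group, with bands for more than 7 and more than 20 days. The woman in Step 3 appears there. This stands, and it makes the point one about the AE table rather than about data collection. It does not close the gap: those tables do not compare a woman with her own baseline, and they do not feed the TEAE incidence.

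Other parts of the reply also stand. The sentence sending bleeding TEAEs to the overall summary is in SAP 11.5.1 and is not repeated in 11.5.2, so pooling is an inference, though a sound one through 11.2. Crude incidence over unequal follow-up is hard to compare under any definition, Mirena is only an informative comparator, and no formal tests are planned. Recruitment was planned to end in April 2013, so the 24-month bleeding diaries would have ended about April 2015. Redefining the early TEAE as the main analysis would now be done with those data in hand.

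A reader might infer more than the documents support:
- *That only heavier bleeding counts before Month 24.* It does not; serious, removal-causing and unrelated events count through the AE CRF.
- *That the gap covers two years of peak irregular bleeding.* Protocol 7.1.7 supports the first 3-6 months, with bleeding and spotting days declining over the first year.
- *That the table must show an artificial rise after Month 24.* A daily prompt may elicit more reports than a three-month recall, and some women may mark heavier for bleeding on an unexpected day. The net direction across Month 24 is not known.
- *That cramping is affected to the same degree.* The cramping box in SAP 11.4.1 asks whether cramping is worse, which is less clearly limited to intensity.

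**Conclusion.** The point holds as a matter of definition. In Months 1-24, non-serious, IUS- or menses-related bleeding that is longer or more frequent, not marked as heavier, and does not lead to removal is not a TEAE. From Month 25 the same bleeding is one, in line with Protocol 7.7. The single bleeding TEAE percentage therefore follows no one definition, and it omits frequency-only worsening in the 3-6 months when irregular bleeding is expected.

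That such events are excluded follows from the text. How many there are does not; the 5 to 30 points above are an illustration, not an estimate. The conclusion rests on reading SAP 11.2 and 11.5 as one pooled summary. The Pearl Index and the other efficacy results are unaffected. The change should be made, but it concerns AE reporting only.

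**What to change.** In SAP 11.2, 11.4 and 11.5:
- Present bleeding TEAE incidence in separate rows for Months 1-24 and Month 25 onward, and do the same for cramping.
- State in each row or its footnote the definition that applied.
- Use the subjects at risk in that period as the denominator of each row.
- Do not report a single pooled percentage for these terms without the split.
- Cross-refer to the SAP 11.6.1 tables for bleeding days in Months 1-24.

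As a sensitivity analysis, add a diary-derived frequency or duration criterion for Months 1-24, with its threshold written into the SAP before it is applied. This depends on the Menstrual History CRF holding a usable baseline for duration or frequency. Protocol 7.12.1 asks sites to verify worsening against Menstrual History, which suggests that it may, but neither document confirms a days-per-interval value. If there is none, the split rows alone are enough.

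The cost is some SAP wording and extra table rows, with no new data collection. The sensitivity analysis, if run, is likely to show a somewhat higher early bleeding AE incidence, which should be explained beside it.
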